3.16 Ethic Approval & Application

The ethical approval of the study was obtained from the Medical Ethics Committee, Faculty of Dentistry, UM [DF CO2301/0007 (P)] on 16th January 2023 as attached in Appendix. The study will also gain the ethical approval from the Medical Research and Ethics Committee (MREC) of the National Medical Research Registry (NMRR), National Institutes of Health (NIH), Malaysia.

3.17 Participant Information Sheet and Informed Consent

Participant information sheet (PIS) and informed consent (IF) will be a prerequisite before participants admitted into the study on the screening day. After going through the PIS, participants who refused to provide consent will not be admitted into the study. Nevertheless, the benefits of this study will be emphasized to them.

3.18 Other Related Approvals

An application for permission to conduct the study has been submitted to the Principle Director of Oral Health Program (MOH) Malaysia on 26th January 2023. Thereafter an application will be made to the Sabah State's Deputy Health Director (in-charge of Dental Division).

Upon securing the approvals, a briefing with the aid of Microsoft Power Point slide presentation will be given to all relevant stakeholders of this study to garner their support and cooperation towards this meaningful and noble study.

3.19 Funding

The study will be funded by the Dental Postgraduate Research Grant, University Malaya and other research grants will also be sought after to lessen the high expenditure that will be incurred by the salivary LCMS lab tests and flight travels.

3.20 Data Privacy & Confidentiality

Every reasonable precaution will be taken to ensure the privacy and confidentiality of all information taken. All personal information that is collected will be kept with utmost confidentiality and will only be used for study purposes only.

3.21 Record Keeping, Data Access & Storage

[figure not shown]
All softcopy research data will be kept in the stored in an external hard drive encrypted with a strong password. Extra measures will be taken to keep the hardcopy data safe and confidential in a locked file cabinet in the Department's room.

Only principal investigator and co-investigators will have access to participant's research data. Study findings will be shared with participants upon request. All data will be kept for a minimum of 3 years after study completion and hence after destroyed.

3.22 Publication Policy

Research findings would be disseminated through academic papers, conference presentations or other means. Extra care would be taken to anonymize any identifiable information prior to dissemination.

3.23 Flow Chart of Research Activities

3.24 Gantt Chart of Research Activities

	YEAR 2											
Year	2022								2023			
Task	M	J	J	A	S	O	N	D	J	F	M	A
Conceptualization of study	√	√										
Further conceptualization on the research methodology			√									
Research proposal preparation & defense				√	√	√						
Application for Ethics, Grants and to MOH & other parties							√	√	√	√		
Phase 1 Adaptation of Questionnaire, Educational Booklet, and Intervention Module											√	
Validation of the Adapted Questionnaire, Educational Booklet, and Intervention Module											√	
Translation of the Validated Questionnaire, Educational Booklet, and Intervention Module												√
Training of the Main Researcher					√	√	√	√	√			√

	YEAR 3									
Year	2023					2024				
Task	M	J	J	A	S	O	N	D	J	F
Phase 2										
Village selection & recruitment (Inclusive of meeting with village head for Pre-test Village)	√									
Pre-test	√									
Recruitment & Training of the Facilitators	√									
Meeting with Village Head & Preparation for Pilot Test	√									
Pilot test		√								
Training of the Facilitators			√							
Phase 3			√							
Promotional Initiatives			√							
Implementation of the study & Data collection			√	√	√					
Data entry						√				
Data analysis						√				
Report writing							√	√		
Manuscript writing									√	
Report submission										√

3.25 Milestones and Dates

Activities	Dates	Progress
Research Proposal Presentation & Defence	11 th October 2022	Completed
Application for Ethics Approval i) Medical Ethics Committee, Faculty of Dentistry, University of Malaya ii) Medical Research and Ethics Committee (MREC) of the National Medical Research Registry (NMRR), National Institutes of Health (NIH), Malaysia	23 rd November 2022 January-February 2023	Completed In Progress
Application for Grants to Fund Study i) Dental Postgraduate Research Grant (DPRG) 2022 ii) NIH Grant on Special Interest (NOSI): Dissemination and Implementation Science for Cancer Prevention and Control in Low Resource Environments (Notice Number: NOT-CA-22-038) iii) NIH Malaysia	December 2022 January-February 2023 February 2023	Completed (Waiting for call of meeting letter) Completed (Had a brief meeting with NIH Global Health Program Director on 2.2.23) In Progress
Application for Permission to Conduct Study and Usage of Facility and Manpower i) Principle Director of Oral Health Program (MOH) of Malaysia ii) Sabah State's Deputy Health Director (in-charge of Dental Division) iii) Kota Belud District Dental Officer	January-February 2023	Completed (Awaiting reply)

Activities	Dates	Progress

Phase 1
 
Cross-cultural adaptation of Questionnaire, Educational Booklet, and Intervention Module
 
Validation of the Adapted Questionnaire, Educational Booklet, and Intervention Module
 
Translation of the Validated Questionnaire, Educational Booklet, and Intervention Module
 
Finalisation of Translated Questionnaire, Educational Booklet & Intervention Module
	
March 2023 (Week 1-2)
 
March 2023 (Week 3-4)
 
April 2023 (Week 1-2)
 
April 2023 (Week 3-4)
	

Training of the Main Researcher
 
1. Questionnaire Design and Validation Workshop ~
 
2. Kuala Lumpur Nicotine Addiction International Conference
 
3. Qualitative Research Methodology & Data Analysis Using Atlas Ti V22 Workshop
 
4. Effective Thesis Writing
 
5. Cognitive Behavioural Therapy (CBT) on Substance Abuse
 
6. One-to One Training with BENIT Principal Researchers (AP [name] & AP [name])
	
29th September 2022
 
3rd October 2022
 
12-13th November 2022
 
29th & 30th November 2022
 
29th & 30th November 2022
 
April 2023
	
Completed
 
Completed
 
Completed
 
Completed
 
Completed
 
In Progress

Phase 2
 
Village selection & recruitment (Inclusive of meeting with village head for Pre-test Village)
 
Pre-test
	
May 2023 (Week 1)
 
May 2023 (Week 2)
	

Activities	Dates	Progress
Recruitment & Training of the Facilitators	May 2023 (Week 3)	
Meeting with Village Head & Preparation for Pilot Test	May 2023 (Week 4)	
Pilot test	June 2023 (Week 1-3)	
Modification to the Questionnaire, Educational Booklet, Intervention Module & others based on findings of Pilot Test	June 2023 (Week 4)	
Training of the Facilitators	July 2023 (Week 1)	
Phase 3 Promotional Initiatives	July 2023 (Week 1)	
Implementation of the study & Field Data collection	July-September 2023	
Data entry	October 2023 (Week 1-2)	
Data analysis	October 2023 (Week 3-4)	
Report writing	November-December 2023	
Candidature Defence	January 2024	
Manuscript writing	January 2024	
Report submission	February-March 2024	

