3.0 MATERIALS AND METHOD

3.1 Overview of the Study design

This is a comparative prospective community trial which utilises a cluster randomised controlled trial design involving a Bajau indigenous community in Sabah, Malaysia with a 1:1 allocation ratio. The clusters are Bajau villages that practises BQ chewing habits in Kota Belud district in Sabah. The Bajau villages are the unit of randomisation. There are 39 Bajau villages in Kota Belud, Sabah (Tahir Z et al., 2003).

The clustered randomised controlled trial study design was selected as there was a high tendency of crossover if both intervention and control groups are randomised within the same village. Individuals allocated to a control group may inadvertently receive some aspects of the intervention if they are in proximity to the individuals in intervention group (Hahn S et al (2005). Thus, clustered randomised trial is the best available design for researchers who evaluating intervention that operates at group level, that manipulates the social and physical environment and cannot be delivered to individual participants without any substantial risk of contamination (NIH, 2022).

The eligible villages will be randomised into intervention and control groups based on the required sample size. The intervention group will receive an educational booklet and a structured BQ cessation program which will be cross- culturally adapted first based on a clinical trial (BENIT) by Paulino YC et al. (2020) for a Malaysian high risk population. The control group will only receive an educational booklet.

Baseline information on participant's demographics, BQ chewing behaviours, BQ composition, BQ dependency levels, reasons for chewing, the readiness and self perceived barriers to cease habit will be obtained prior to the commencement of the intervention. The

same participants will be followed-up at 22-day and 3-month after commencement of intervention to assess their of quitting experience and impact of the intervention. Day 22 follow-up was kept in this study as it will enable study results to be compared with similar BQ cessation studies in other parts of the world such as in Pacific Islands (Moss J. et al., 2015 and Paulino YC et al., 2020).

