3.10.3 Phase 3 Implementation of the study (Field Work)

3.10.3.1 Initiatives to promote study

Prior to the start of the intervention, a **promotional initiative** will be conducted with the village head 3 weeks before the implementation of the study. The purpose of this promotion is to provide knowledge and convince the village head regarding the ill effects of the chewing habit. By agreeing and cooperating to this intervention, his villagers will receive the very first kind of such an intervention in Malaysia to curb the villager's 'addiction'. With adequate knowledge and a right attitude, the village head can have a positive predisposition to encourage his villagers to participate in this beneficial program. Once the trust of the 'strongman (the village head) has been gained', it will be easier to conduct the multi-component intervention in those villages.

Attractive posters and flyers will be distributed to the village head to paste in the allowed public places and for door-to-door flyer dissemination to ensure the villagers are aware of the intervention on the said date. The intervention will be carried on a weekend to obtain maximum participation.

One week before the implementation of the study, villages will be reminded of the program date and villagers who practises BQ habits will be advised to attend the intervention together with family members, relatives or neighbours who also has the similar habit. Moss J et al. (2015) claimed intervening the surrounding community with the similar risk habits can ensure the long term sustainability of habit cessation among chewers.

The first day of the program will be the screening day.

[figure not shown]
[figure not shown]

Figure 3.5 Summary of Promotional Initiatives

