The community screening program for the intervention group will be organised at the community hall on a Saturday. Villagers who attend the screening program will first be registered and screened for eligibility to participate in the study (**Checkpoint 1**). The eligible participants will be briefed on the nature of the intervention and will be invited to participate. A copy of 'Patient Information Sheet' (PIS) (Appendix A) will be given for the reference about the study details and written informed consents (Appendix B) will be obtained from the villagers prior admitting them into the study.

Only consented participants will be interviewed by the trained interviewers (**Checkpoint 2**). Face-to-face interviews will be carried out to gain participant's information regarding demographics details and baseline information of BQ chewing behaviours, BQ composition, BQ dependency levels, reasons for chewing, readiness and self-perceived barriers to quit habit. No intra-oral clinical examination will be carried out in this study.

Upon completion of the interview, participants will be briefly explained and given an educational booklet which contains general information regarding AN and BQ, risk associated with BQ chewing behaviour, cessation strategies that are modeled after tobacco cessation and researcher's contact information. They will then be ushered to saliva collection counter (**Checkpoint 3**) to provide their baseline saliva sample.

Participants will be thanked and given a token of appreciation before being ushered out of the community hall and will be reminded to return the next day (Sunday) to initiate the first support session for the cessation intervention. For every intervention session attended by the participants, they will be monetarily incentivized for their time and commitment for cessation. Appointment card will be provided to ease participants reference of support session dates.

A self explanatory video presentation regarding general information of AN and BQ, the ill health effects of BQ and introduction and importance of cessation program will be continuously played **for the non- chewers in the village hall** to increase their knowledge and awareness while they are waiting for their family members. who are undergoing the screening. This can help maximise their support for their loved ones who are trying to quit the risk habit.

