Later, a discussion on the overall quitting experience will ensue. Participants who have relapsed and started chewing but are willing to attempt to quit again will be encouraged. **Strategies for managing thoughts** that could lead to relapse will be introduced. The participant's lifestyle changes that supports quitting will be reviewed. Usage of "excuses" for not chewing and employing "fake chew" will be reinforced.

The **Positive and Negative Thoughts Worksheet (Appendix L)** will be a strategy to manage the thoughts that participants might have through their quitting journey. This method is based on the notion that mood is related to the balance of the positive and negative thoughts. When negative thoughts outweighed the positive thoughts, the result is a depressive, anxious, angry or other symptoms that precipitate the behaviour of risk habit such as chewing to overcome it (Brown RA et al. 2003). The thoughts with a clear message of positivity or negativity should be recorded and it is curcial to discern which type of thoughts dominates in this process. The negative thoughts can be managed with the coping skills that they were thought before. The main researcher will brief all participants regarding this thought management through a talk.

Checkpoint 2 will be prepared for completion practice for Positive and Negative Thoughts worksheet (Appendix L). One of their current positive and negative thoughts will be used as a practice. At the end of session 5, **Checkpoint 3** will be prepared as saliva collection counter for participants to provide their 22-day saliva samples.

[figure not shown]

Figure 3.12 Summary of Participants' Flow on the 5th Session of the Intervention (Day 22)

3-month follow up (Day 90)

On **3- Month follow up**, participants will be assessed of their chewing abstinence through a follow up questionnaire after registration (**Checkpoint 1**). The items that will be required are brief personal particulars, participant's current chewing status, number of cut-down of habit by the participants (quid/day) and BQ composition if participants are still chewing. All participants will be motivated and encouraged regardless their success in quitting the BQ behaviour. A repeated educational talk of adverse effects of AN and BQ chewing habit will be given. A summary of community perception will be informed to the participants and they will be encouraged to contact research team if they needed any form of help in cessation in the future.

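### The collection window in 3.24 and 3.25 closes about 1 to 5 weeks before the Month 3 visit that the protocol's own intervals imply

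*Protocol*

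**What the plan says.** - **Calendar (3.25, mirrored by month in 3.24).** Facilitator training and promotional initiatives are each dated "July 2023 (Week 1". Implementation with field data collection is dated "July-September 2023". Data entry takes October Weeks 1-2, analysis is dated "October 2023 (Week 3-4", report writing follows in November-December 2023, and submission in February-March 2024.
- **Lead time (3.10.3.1).** The promotional initiative "will be conducted with the village head 3 weeks before the implementation of the study". The same section adds: "The first day of the program will be the screening day".
- **Day of the week (3.10.3.1 and 3.10.3.2).** The programme runs on a weekend. For intervention villages, screening is "organised at the community hall on a Saturday" and is labelled Day 0.
- **Last visit (3.1 and 3.10.3.2).** Participants are "followed-up at 22-day and 3-month after commencement of intervention"; the visit is headed "3-month follow up (Day 90".
- **Role of Month 3 (1.7, 3.12).** The null and alternative hypotheses refer only to the 3-month assessment. Day 22 and Month 3 are both primary outcome time points, and saliva biomarkers are measured at both.

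**The concern.** Each date looks reasonable alone. The difficulty appears when the July Week 1 promotion is combined with the three-week lead and the 90-day follow-up. Those intervals push the last visit into the second half of October, when the timetable has already finished collection and data entry and has moved to analysis.

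At stake is the one comparison named in the hypothesis. A timetable that closes collection before that visit gives the field team, the laboratory and the analyst inconsistent instructions about when the data set is complete. Month 3 saliva also has to be transported and assayed before its results can be entered, and the timetable leaves no time for that after an October visit.

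**Working it through.** **Inputs.** Promotion in July 2023 Week 1, read as 1-7 July or alternatively 3-9 July (3.25); lead of 21 days (3.10.3.1); Saturday screening as Day 0, and last visit at Day 90 (3.10.3.2); window 1 July to 30 September (3.25). 1 July 2023 is a Saturday.

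**Window alone.** 1 July to 30 September spans 91 days. The latest Day 0 that allows Day 90 inside it is 30 September − 90 days = 2 July. So the length of the window does not by itself exclude the visit.

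**Adding the protocol's intervals.** Day 0 = promotion date + 21 days, moved to the next Saturday where needed. Month 3 = Day 0 + 90 days.

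| Reading | Day 0 | Day 90 | Days after 30 September | Slot in 3.25 |
|---|---|---|---|---|
| Promotion 1 July, with lead | 22 July | 20 October | 20 | Analysis |
| Promotion 2-8 July, with lead | 29 July | 27 October | 27 | Analysis |
| Promotion 9 July (Week 1 as 3-9 July), with lead | 5 August | 3 November | 34 | Report writing |
| Lead ignored, first Saturday after 1-7 July | 8 July | 6 October | 6 | Data entry |

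**Variants.**
- Without the move to Saturday, promotion on 1-7 July gives Day 0 on 22-28 July and Day 90 on 20-26 October.
- Counting three calendar months from a 22 or 29 July screening gives 22 or 29 October.
- Ignoring the lead with Week 1 read as 3-9 July, the first Saturday afterwards is 15 July, and Day 90 is 13 October.

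**What would fit.** Day 0 on 1 July gives Day 90 on 29 September; Day 0 on 2 July gives 30 September. With the lead, promotion would have to be no later than 2 July − 21 days = 11 June. The timetable has the pilot test running then (June Weeks 1-3) and promotion only in July Week 1.

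**Day 22.** From 22 or 29 July it falls on 13 or 20 August, inside the window. Only Month 3 is displaced.

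The table assumes that all villages start on the same weekend. Staggering them, or spreading groups across the week as 3.10.3.2 does, moves the last Month 3 visit later.

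**The case against.** The strongest reply has four parts.

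1. **The window is long enough.** This stands as arithmetic: 91 days can hold a Day 90 visit. It would be too strong to say that July-September cannot contain the visit. The conflict comes from adding the July Week 1 entries and the lead time. The promotion entry is the firmer of the two July constraints, because 3.25 also lists facilitator training in May.
2. **The July Week 1 promotion line may not be the three-week step.** Section 3.10.3.1 describes promotion in stages: the village head, posters and flyers, then a reminder one week before. The milestone row does not say which stage it marks. This also stands, and it is why the shortfall is a range. The three-week reading is the more natural one, and dropping it still leaves Day 90 on 6 October.
3. **No data need be lost.** A reader might infer that the hypothesis would be tested without its data, or that the visit would be pulled forward to about Day 63-70 (29 or 22 July to 30 September). The documents support neither. Visit timing is fixed by the procedures: 3 months in 3.1, appointment cards and Day 90 in 3.10.3.2. The ordinary result is that data entry and analysis start late. Day 22, also a primary time point, is unaffected.
4. **These are provisional project dates.** Some approvals were still pending in 3.25, and submission is not due until February-March 2024. That limits the severity. It does not make the stated dates consistent with the visit schedule.

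**Conclusion.** The timetable in 3.24 and 3.25 is inconsistent with the protocol's own lead time and visit schedule. On the natural reading, Month 3 falls on 20 or 27 October, about 3 to 4 weeks after collection closes, after data entry and inside the analysis slot. Across the readings considered, the shortfall runs from 6 days (about 1 week, within data entry) to 34 days (nearly 5 weeks, past the analysis slot).

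This rests on the stated calendar weeks, a Saturday Day 0 and simultaneous village starts; staggered starts would lengthen it. It is a scheduling contradiction that touches the hypothesis time point. It does not in itself change any estimate, error rate or power, provided the visit stays at Day 90 and analysis waits for it.

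**What to change.** Reconcile 3.10.3.1, 3.10.3.2, 3.24 and 3.25:

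- Extend field data collection through the Month 3 visit of the last participant in the last village, and keep that visit at Day 90.
- Start final data entry and analysis only once those interviews and the Month 3 saliva results are available, and move report writing accordingly.
- Tie these steps to the last Month 3 visit, not to a fixed date. The end of October would be too early if Week 1 means 3-9 July or if villages are staggered.
- State which promotional step the July Week 1 entry marks.

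The cost is a few weeks on the timetable, with no change for participants or to study procedures.

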4.0 EXPECTED RESULTS/BENEFIT

i. Novel theories/New findings/Knowledge

This study would be able to provide new and updated knowledge on the demographics of BQ chewers, BQ chewing behaviours, BQ composition, BQ dependency levels, reasons for BQ chewing, the readiness and self-perceived barriers to cease BQ habit among Bajau BQ users in selected high-risk communities in Kota Belud, Sabah, Malaysia.

Another crucial new finding that can be garnered from this study is the usage of saliva bio verification procedures to verify the self-reported outcomes from the BQ cessation program conducted within the high-risk communities. This will be the first conducted in Malaysia thus far.

ii. Research Publications

A minimum of 2 research publications are targeted to be produced by this study. A paper on the cross-culturally adapted BQ cessation program and its pilot test findings. Another paper on the implementation of the BQ cessation program and verification of the program's effectiveness with a saliva test.

iii. Specific or Potential Applications

This study will significantly facilitate the Oral Health Program of the Ministry of Health (MOH), Malaysia and other organisation with the an introduction of the first BQ cessation program for Malaysian high risk communities which have been long neglected.

In the long run, through continuous and wider execution of this cesation program, it could help to reduce the high prevalence of BQ chewing practices in Malaysia. Apart from that, the

BQ users would also be finally able to experience a formal cessation program to curb their addictions.

iv. Intellectual Properties (if any)

A newly adapted Betel Quid Cessation Program for high-risk communities in Malaysia.

